**2. Lay summary**

Bipolar disorder (BD) is a serious, disabling, and highly recurrent illness that is disproportionately represented in the criminal justice system. BD increases risk for several adverse outcomes for prisoners, including mood instability, suicide attempts, substance use relapse, and high rates of repeat incarceration. Despite these serious negative consequences, up to 70% of prisoners with BD do not receive mental health treatment upon prison release. Lack of engagement in ongoing mental health treatment for BD upon community re-entry represents one potent factor that perpetuates risk for adverse outcomes, and consequences of untreated BD (e.g., impulsivity, substance use) may greatly exacerbate difficulties in establishing stable living conditions (e.g., adequate housing, legal employment) at community re-entry. Thus, there is a critical need for interventions to facilitate engagement with treatment for BD during this vulnerable transition.

The primary aim of this pilot trial is to develop and establish the feasibility, acceptability, and potential for future uptake of the Community treatment Adherence at Re-Entry (CARE) program. CARE is an innovative intervention that will combine evidence-based cognitive-behavioral, family, and telephone outreach strategies to promote treatment engagement and improve clinical outcomes for prisoners with BD during the period of community re-entry. CARE will include 3-4 individual sessions in prison or in the community, 1 optional family session, and 11 brief telephone contacts for up to 6 months. Given its moderate intensity, adjunctive nature, use of community mental health counselors, and use of telephone administration for post-release follow-up, CARE has been designed with an eye toward community implementation. Its proposed mechanisms of action (i.e., increasing values-action consistency, enhancing social supports, and linkage to community treatment services) are further well matched to the practical and clinical needs of re-entering individuals.

The development phase of the study will result in a treatment manual, training manual, and fidelity scales, to be tested in an open trial of 12 prisoners with BD nearing prison release. The pilot study phase will examine the feasibility and acceptability of the proposed recruitment methods, research design, intervention, and training program by randomizing 40 prisoners with BD nearing prison release or recently released to treatment as usual (TAU), enhanced with monitoring and emergency referral, or to enhanced TAU plus CARE. The primary outcome will be mood symptoms in the 6 months follow-up window. Secondary outcomes include: suicidal ideation/behaviors, substance use, re-arrest rates, and employment and housing stability. We will also explore differential engagement of CARE's purported mechanisms of action. To our knowledge, this proposal represents the first attempt to develop and pilot a targeted transitional intervention for BD among prisoners, laying the groundwork for a larger clinical trial (R01) to evaluate the effectiveness of CARE for improving clinical outcomes for this seriously ill, high risk, understudied population during the vulnerable transition from prison to community re-entry.

**3. Protocol narrative**

Please note: We have approval from the [REDACTED] to conduct human subjects research at their site. In addition, the [REDACTED] IRB submitted this protocol to the U.S. Office of Human Research Protections (OHRP) for their certification of this research protocol.

**3a. Aims:**

The primary aim of this pilot effectiveness trial is to develop and establish the feasibility, acceptability, and potential for future uptake of CARE (Community treatment Adherence at Re-Entry), an innovative, moderate intensity intervention that combines evidence-based cognitive-behavioral, family, and telephone outreach strategies to promote community treatment engagement and thereby improve clinical outcomes for prisoners with bipolar disorder (BD) across the period of community re-

entry. Development of CARE will be informed by our experiences successfully piloting a similar intervention (the Integrated Treatment Adherence Program; ITAP) for individuals with BD and comorbid substance dependence across another vulnerable transition, from inpatient to outpatient care in the community. As an adaptation of ITAP for community re-entry, CARE will be designed to be delivered by a range of clinicians, providing advantages for scalability in the resource-poor criminal justice system. Its proposed mechanisms of action (i.e., increasing values-action consistency, enhancing social supports, and linkage to community treatment services, all to promote treatment engagement, thereby improving clinical outcomes) are further well-matched to the practical and clinical needs of re-entering individuals.

The secondary aim of this research will be to compare outcomes, within 95% confidence intervals, between CARE as an adjunct to treatment as usual (TAU) vs a TAU control condition. In keeping with ethical obligations, we will enhance TAU by providing post-release monitoring and emergency referral, as needed. We will explore future dissemination potential by using community mental health counselors for treatment delivery.

The *development* aims of this project are to:

- 1) Develop a comprehensive treatment manual, interventionist training program, and fidelity scales for CARE, comprised of 3-4 individual sessions prior to release, and 1 family meeting (when applicable), followed by a series of 11 brief telephone outreach contacts up to 6 months post-release.
- 2) Improve the clarity, content, acceptability, and feasibility of CARE through a small open trial (n=12) of prisoners with BD treated through 6 months post-release, followed by stakeholder interviews (participants, prison staff, community mental health partners) as part of the refinement process.

The *pilot study* aims of this project are to:

- 3) Conduct a randomized pilot trial in 40 prisoners with BD, comparing CARE to TAU to demonstrate the *feasibility* and *acceptability* of the proposed recruitment methods, research design, intervention, and counselor training program, with assessment at baseline, pre-release, and 1 and 6 months post-release. For those recruited post-release, assessments will be at baseline, 1 month and 6 months.
- 4) Examine 95% confidence intervals around differences between CARE and TAU for the following outcomes: reduced mood symptoms (*primary*); suicidal ideation and behaviors, substance use, rates of re-arrest, and more stable employment and housing (*secondary*);
- 5) Examine 95% confidence intervals around differences between CARE and TAU to evaluate differential engagement of purported mechanisms of action: increased values-action consistency, practical and emotional social support, and increased treatment engagement (i.e., utilization and adherence).

### **3b. Methodology:**

#### **3.b.1. Description of study participants.**

Participants will be sentenced prisoners who are incarcerated in the women's and men's minimum and medium security prison facilities at the [REDACTED]. In the development (open trial) phase, we will consent up to 36 prisoners in order to achieve our enrollment goal of 12 prisoners who meet study inclusion criteria for participation. In the pilot trial phase, we will consent up to 160 prisoners in order to achieve our enrollment goal of 40 prisoners who meet study inclusion criteria for randomization to conditions. Additional inclusion criteria across both phases include: 1) DSM-5 diagnosis of bipolar I, bipolar II, bipolar disorder not elsewhere classified, or schizoaffective disorder, bipolar type, as determined by the Structured Clinical Interview for DSM-5 Disorders (SCID-5); 2) 18 years or older; 3) Anticipated prison release within 4-10 weeks or recent prison release; 4) Expected release to or current living in locations anywhere within [REDACTED]; and 5) Willingness to sign an informed consent [REDACTED]

document that describes study procedures. Exclusion criteria include: 1) Presence of current psychiatric symptoms severe enough to warrant separation from the general prison population; 2) Cognitive impairment sufficient to prevent successful completion of the baseline interview; and 3) Inability to understand sufficiently well to understand the consent form or assessment instruments when they are read aloud. Virtually all prisoners at the [REDACTED] speak English. Because a few prisoners may have reading difficulties, consent forms will always be read aloud and RAs will offer to read self-report measures aloud. As CARE is designed to be purely adjunctive and because release dispositions can change dramatically in the days leading up to release, participants will not be included/excluded based on post-release treatment plans (or lack thereof).

Those assigned to receive the CARE intervention (n= 12 in the open trial; n = 20 in the pilot randomized trial) will be invited to have a family member or significant other (heretofore referred to as SO) participate in the intervention with them. We highlight that this is not a requirement for participation of the prisoner participant, but will be optional. Hence, we will enroll up to 32 SOs into this study. In order to be eligible for participation, SOs must be over 18, speak and read English, have frequent (at least every other week) contact with the prisoner participant, be on the prisoner participant's visitor list at the [REDACTED] (for those prisoners recruited while still incarcerated), and consent to participate in treatment.

Finally, as part of the treatment development process, we will conduct brief (~30 min) stakeholder interviews with relevant parties (e.g., [REDACTED] staff and administrators, community mental health partners). We anticipate conducting up to 6 interviews with relevant stakeholders (2 each with [REDACTED] staff, administrators, and partnered community mental health center administrators), half of which will occur upon completion of the open trial and half of which will occur upon completion of the pilot randomized trial. In order to be eligible to participate in this interview, individuals must be: 18 years or older, currently employed in one of the stakeholder settings described above, able to speak English sufficiently well to participate in the interview, and to consent to participate in the interview.

Special classes. Because the purpose of this study is to develop and evaluate the feasibility and acceptability of CARE in prisoners during the vulnerable period of community re-entry, it is necessary to sample a prison population. Prisoners are an understudied population with complex treatment needs; hence the urgency for more research attending to the mental health concerns of this population. Incarcerated children 18-21 will be eligible. Recruitment procedures are described in more detail in the "Protection of Human Subjects" section.

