In the Pilot Randomized Trial Phase, if a participant is determined to be eligible following the baseline assessment, s/he will be randomized to either E-TAU plus CARE or to E-TAU alone.

**Randomization** will be determined in a 1:1 ratio, with 2 stratification variables, the maximum number advisable in a sample of this size: sex (male vs. female) and polarity of most recent mood episode (depression vs. (hypo)mania) using a randomization table.

Participants randomized to receive CARE will receive 4 counseling sessions. The first 3 sessions will be individual sessions that take place in prison in the time between the baseline assessment and the anticipated date of release from prison; or they will take place after release for those enrolled post-release. A fourth session will either be an individual counseling session or a family/SO session (as applicable). This session will take place either in prison prior to release or as soon as possible after release either by telephone, by zoom, or in person (e.g., at our offices or in any residential facility where the participant is located, with facility approval). Ideally, the first two sessions will be delivered within 1 week, the third session will be delivered within the following week, and the fourth session will be delivered within the week after that as either an individual session or a family/SO session. However, we acknowledge that time to release will be variable, and the session schedule may be compressed or spread out depending upon length of time available to complete the sessions between the baseline assessment and the prison release date. Following prison release (in prison enrollment) or completion of the initial sessions (post-release enrollment), the counselor will initiate the phone follow-up calls, delivered across the first 6 months post-release (in prison enrollment) or 6 months post-baseline (post-release enrollment). The schedule for phone follow-up will be: weekly for the first month, biweekly for the next 2 months, and then monthly for the final 3 months. Calls will be made separately to the prisoner participant and to the identified SO (if applicable).

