### **3.b.9. Data analysis.**

For this pilot effectiveness study, assessment of feasibility and acceptability of the intervention and research procedures is the primary goal. Nonetheless, pilot data can be used to demonstrate whether the effects of treatment look promising across a set of outcome variables, to begin to examine distribution of outcome variables to inform future analytic strategies, and to suggest, in concert with results from larger scale clinical trials in related fields, the range of effect sizes that would be reasonable to expect in a future trial.

Study Feasibility and Treatment Feasibility/Acceptability. One of the primary goals of a pilot study is to demonstrate the feasibility of the proposed treatment and of the study and recruitment methods. As a result, we will assess the feasibility of the research procedures by examining study recruitment and refusal rates, participants' willingness to be randomized, follow-up rates, reliability and range of responses to study questionnaires, and success of the interventionist training program. We will assess the feasibility and acceptability of CARE by examining rates of treatment attendance, rates of treatment completion (attending at least 3 of the 4 initial sessions and completing 6 out of the 11 scheduled post-release telephone calls) and drop-out, and reports on the End of Intervention Questionnaire. We will also examine reasons for termination for consistent patterns. We will examine the acceptability of both CARE and E-TAU using data from CSQ-8 treatment satisfaction and end of intervention questionnaires and detailed exit interviews.

Primary Outcomes: Using multilevel modeling of group by time, we will calculate the effect size and 95% CI for percent time symptomatic using the LIFE, with percent time symptomatic in the 90 days prior to study enrollment as a covariate. We will calculate similar exploratory tests for symptom severity using the QIDS and ASRM total scores, with baseline scores as covariates.

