### **3.c.6. Safety Monitoring Plan**

[REDACTED] will be responsible for overseeing the safety of all participants. [REDACTED] (who maintains her clinical license in RI) will be available to serve as clinical back-up for [REDACTED], when required. [REDACTED], study co-investigator, is a board-certified psychiatrist who will serve as the medical advisor. Participant safety will be monitored in two ways: (a) during the intake or ongoing assessments by the research staff, or (b) during intervention sessions. Research assessments will be conducted in the prison at study intake, at pre-release (4-10 weeks later), and in the community at 1 and 6 months post-release. We will monitor all participants for significant suicidal ideation (SI), homicidal ideation (HI), and clinical deterioration at each time point.

**During incarceration** the [REDACTED] standards for mandatory reporting of suicide risk specify that we are required to report anyone who has had suicidal ideation within the past 24 hours (as determined by a QIDS item 12 score > 1, LIFE PSR > 2, or reporting any current desire to hurt oneself to any member of the research staff). If the participant reports this level of SI within the past 2 weeks, but not in the 24 hours prior to the assessment, a voluntary referral will be offered. Participants meeting the prison's SI mandatory reporting criteria (or those who elect the voluntary referral) will be referred to a prison mental health clinician for evaluation, who will follow prison procedures. Standard prison procedures include: (1) checking in the prison's electronic medical record to see if the person has already been flagged as having SI; (2) having a licensed mental health clinician check in with the person and do a suicide risk evaluation; and/or (3) if needed, putting the person on psychiatric observation within the prison. If the prison mental health professional determines that someone's risk has gone down, that person will leave

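### The pilot enrols by two routes with different clocks, settings and visit counts, but the analysis has no route term and pools the feasibility measures, so it cannot show which route was feasible.

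*Combined protocol and SAP*

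**What the plan says.** Section 3.b.1 admits people by either of two routes: "Anticipated prison release within 4-10 weeks or recent prison release". The first has a window in weeks. The second has none, either there or in the post-release recruitment text of 3.b.5, which says the route was added because of the pandemic.

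The routes are then handled differently:

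- **Clock.** In 3.b.6, calls and follow-up visits run from release for prison enrollees and from baseline for post-release enrollees. Section 3.b.8 instead places the post-release group's follow-up at 1 and 6 months after release.
- **Setting.** In 3.b.2 and 3.b.6, the first three sessions are planned in prison for one route. For the other they take place after release, by telephone, by zoom or in person.
- **Assessments.** Prison enrollees have four. Post-release enrollees have three, because they have no pre-release visit (3.b.6 and the note to Table 2).

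Allocation "will be determined in a 1:1 ratio, with 2 stratification variables, the maximum number advisable in a sample of this size". The factors are "sex (male vs. female) and polarity of most recent mood episode".

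The primary analysis in 3.b.9 reads "Using multilevel modeling of group by time, we will calculate the effect size and 95% CI for percent time symptomatic using the LIFE". It adjusts for the same measure taken over the 90 days before enrolment. The secondary models follow the same pattern, and re-arrest is compared by chi-square. No model names route, and no feasibility measure is split by it. The mechanism analysis assumes four time points for everyone.

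**The concern.** Section 3.b.9 makes feasibility the primary goal, and pilot aim 3 in 3a extends it to the recruitment methods and research design as well as the intervention. The pilot has two recruitment methods and two delivery settings. A single refusal, attendance, completion or follow-up rate averages over both. If one route recruits or retains well and the other badly, the pooled figure describes neither, and the later trial could not use it to choose a route.

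For the outcome models there are two lesser problems. Route is plausibly prognostic, so leaving it out costs some precision and leaves any chance imbalance between arms unadjusted. Also, a time axis that starts at release for some participants and at baseline for others, with the origin unstated, makes the group-by-time term hard to interpret.

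**Working it through.** The plan gives no power or precision calculation, so there is no figure to reproduce. The stated inputs are N = 40, 1:1 allocation and 20 to CARE (3.b.1, 3.b.6). The route mix, the route effect and days since release are not stated. They are assumed below and shown as ranges.

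**1. What the clocks imply.** Take 6 months as 183 days and let X be days from release to a post-release baseline. Under 3.b.6 the final visit falls at 183 + X days after release. Follow-up covers (183 − X)/183 of the first six months, and X/90 (at most 1) of the 90-day baseline window is community time.

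| X (days) | Final visit, days after release | First 6 months covered | Baseline window in community |
|---|---|---|---|
| 0 | 183 | 100% | 0% |
| 30 | 213 | 84% | 33% |
| 60 | 243 | 67% | 67% |
| 90 | 273 | 51% | 100% |

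Prison enrollees reach the final visit about 183 days after release. With 4 to 10 weeks from baseline to release, that is 28 + 183 = 211 to 70 + 183 = 253 days after baseline.

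Under 3.b.8 the final visit stays at 183 days after release for everyone. But for anyone enrolled 30 or more days after release, the 1-month visit falls on or before baseline. The two sections therefore give materially different schedules.

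**2. Intervention received by the 1-month visit.** At the ideal pace in 3.b.6, the initial sessions take about 3 weeks. Prison enrollees have then had those sessions plus about 4 weekly calls. Post-release enrollees, on the baseline clock, have had the sessions plus about 1 call. The same visit label marks different points in the programme.

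**3. Chance imbalance.** Let K of 40 enter after release and let X_C be the number allocated to CARE, hypergeometric (40, K, 20), ignoring the existing strata. The arms differ by |2X_C − K|.

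| K | P(differ by 4 or more) | P(differ by 6 or more) |
|---|---|---|
| 4 or 36 | 11% | – |
| 10 or 30 | 27% | 6.5% |
| 16 | 33% | 10.5% |
| 20 | 34% | 11% |

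A difference of 4 is 4/20 = 20 percentage points, and 6 is 30. With an assumed route effect of 0.5 SD, the arm contrast shifts by 0.20 × 0.5 = 0.10 SD or 0.30 × 0.5 = 0.15 SD.

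**4. Precision.** For a simple two-arm comparison the 95% half-width is t(0.975, 38) × √(2/20) = 0.64 SD. With the same 0.5 SD route effect and a 50:50 mix, omitting route inflates the SD by √(1 + 0.25 × 0.5²) = √1.0625 = 1.03, about 3%.

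**5. What by-route results can bear.** With 10 per arm within a route the half-width is t(0.975, 18) × √(2/10) = 0.94 SD. For a route-by-arm interaction with 10 per cell it is t(0.975, 36) × √(4/10) = 1.28 SD. By-route outcome estimates can only be descriptive.

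**The case against.** The strongest reply is that randomisation balances route on average and the ordinary interval already allows for chance imbalance. A shift of 0.10 to 0.15 SD is small beside a half-width of 0.64 SD, and the pilot has no efficacy decision rule. The route mix is unknown, and because the second route arose when prison access closed, one route may dominate. All of this stands, and it limits the argument about outcomes. It does not touch the feasibility argument, which needs no assumed effect size.

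Leaving route out of the strata is also defensible, since the plan gives its reason for stopping at two factors.

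A reader might infer several stronger points that the documents do not support:

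- **That post-release enrollees fall outside the target.** The lay summary defines CARE as delivered in prison or in the community, and the population as nearing release or recently released. In-prison delivery also has its own 12-person open trial (3.b.6).
- **That the baseline look-back differs by route.** The rule is 90 days for all. Only the setting it covers differs.
- **That post-release sessions are mainly remote.** In-person sessions are allowed, and prison enrollees released early may use the same modes (3.b.2).
- **That anyone re-arrested or unwell soon after release is screened out.** No criterion says so. Reduced reach is plausible, but no more than that.
- **That disclosing suicidality has consequences on one route only.** In custody, "we are required to report anyone who has had suicidal ideation within the past 24 hours". In the community, 3.c.6 also sends any reported ideation to a covering clinician at once.

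**Conclusion.** The concern holds as a gap between design and analysis. The plan runs two enrolment routes that differ by its own account, then analyses and reports them as one. The effect on the arm contrast is modest: a 27 to 34% chance of a difference of four or more post-release enrollees if 10 to 20 of 40 come that way (11% at 4 or 36), and about 3% on interval width under an assumed 0.5 SD route effect and an even mix. Neither figure implies bias in the randomised comparison. The main cost falls on the feasibility aim, because pooled rates cannot be attributed to a route. The conflict between 3.b.6 and 3.b.8, and the reference to four time points when one route has three, are inconsistencies on the face of the text and rest on no assumption.

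**What to change.** In 3.b.9:

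- Add enrolment route as a fixed covariate in the primary and secondary multilevel models.
- State the time origin of those models.
- Report recruitment, refusal, attendance, completion and follow-up descriptively by route.
- For re-arrest, show counts by arm and route, since a simple chi-square cannot take a covariate.
- Correct the mechanism analysis so that it allows for three time points on one route.

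Record days since release at baseline for post-release enrollees and describe the distribution. Reconcile the follow-up schedules in 3.b.6 and 3.b.8.

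The cost is one degree of freedom per model, one baseline field and some wording, since route is already known for everyone. No new stratum is required: a third two-level factor would give eight cells averaging 40/8 = 5 people. Nor is a new eligibility limit on recency, which would be a change to the entry criteria.

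The covariate has limits. A main effect does not align the clocks, and it does not let the baseline slope differ by route. Because the second route was added during the pandemic, a route difference may also reflect calendar time. By-route outcome results should be labelled descriptive.
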